Eligibility	
Inclusion criteria
 
 • Patients must be at least 18 years of age with evidence of relapse or refractory disease as defined by IMWG criteria and measurable disease as defined by any of the following: 
 ○ Serum M-protein ≥ 0.5 g/dl (≥ 10 g/l) ○ Urine monoclonal protein ≥ 200 mg/24h ○ Involved FLC level ≥ 10 mg/dl (≥ 100 mg/l) and an abnormal serum free light chain ratio (<0.26, or >1.65) ○ Measurable biopsy proven plasmacytoma (should be measured within 28 days of registration to study) • Patients must have had at least 2 prior lines of therapy. • Patients must not have had progression of disease on lenalidomide 25 mg. Stable disease on lenalidomide is permitted. • Patient may be enrolled at any time from last line of therapy • Patients must have ANC $> 1000/\mu\text{L}$; Platelets $\geq 75,000/\mu\text{L}$, If plasma cell percentage on bone marrow biopsy aspirate or core is $> 30\%$, platelet eligibility requirement will be adjusted to 60,000/μl. • Patients must have adequate hepatic function as evidenced by: total bilirubin ≤ 1.5 mg/dL, alkaline phosphatase $\leq 3X$ the ULN, AST/ALT $\leq 2X$ the ULN • Patients must have adequate renal function as evidenced by serum creatinine ≤ 2 mg/dL or calculated creatinine clearance of ≥ 40 ml/min within 14 days of registration using MDRD formula. • Patient must be able to swallow capsule or tablet. • Patients must provide informed consent. • Patients must have a left ventricular ejection fraction $> 30\%$, no uncontrolled arrhythmias or New York Heart Association class III-IV heart failure. • Patients must have a Karnofsky performance status ≥ 70. • A negative pregnancy test will be required for all women of child bearing potential. Breast feeding is not permitted. • Fertility requirements 
 ○ Female patients with child bearing potential must have a negative pregnancy test at least 7 days before starting treatment drugs. ○ Male patients must agree to use an adequate method of contraception for the duration of the study and for 90 days afterwards. ○ Female patients must be either post-menopausal, free from menses ≥ 2 yrs, surgically sterilized, willing to use two adequate barrier methods of contraception to prevent pregnancy, or agree to abstain from sexual activity starting from screening and for 90 days afterwards. ○ Female patients of child bearing potential must agree to comply with the fertility and pregnancy test requirements dictated by the Rev-Assist

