3 ELIGIBILITY CRITERIA

3.1 Inclusion Criteria

- Patients must be at least 18 years of age with evidence of relapse or refractory disease as defined by IMWG criteria and measurable disease as defined by any of the following:
 - Serum M-protein \geq 0.5 g/dl (\geq 10 g/l)

- Urine monoclonal protein \geq 200 mg/24h
 - Involved FLC level \geq 10mg/dl (\geq 100mg/l) and an abnormal serum free light chain ratio (<0.26 , or >1.65)
 - Measurable biopsy proven plasmacytoma (should be measured within 28 days of registration to study)
- Patients must have had at least 2 prior line of therapy.
- Patients must not have had progression of disease on lenalidomide 25 mg. Stable disease on lenalidomide is permitted.
- Patient may be enrolled at any time from last line of therapy.
- Patients must have ANC $>$ 1000/ μ L; Platelets \geq 75,000/ μ L, If plasma cell percentage on bone marrow biopsy aspirate or core is $>$ 30%, platelet eligibility requirement will be adjusted to 60,000/ μ l.
- Patients must have adequate hepatic function as evidenced by: total bilirubin \leq 1.5 mg/dL, alkaline phosphatase \leq 3X the ULN, AST/ALT \leq 2X the ULN
- Patients must have adequate renal function as evidenced by serum creatinine \leq 2mg/dL or calculated creatinine clearance of \geq 40ml/min within 14 days of registration using MDRD formula.
- Patient must be able to swallow capsule or tablet.
- Patients must provide informed consent.
- Patients must have a left ventricular ejection fraction $>$ 30%, no uncontrolled arrhythmias or New York Heart Association class III-IV heart failure.
- Patients must have a Karnofsky performance status \geq 70.
- A negative pregnancy test will be required for all women of child bearing potential. Breast feeding is not permitted.
- Fertility requirements
 - Female patients with child bearing potential must have a negative pregnancy test within 7 days before starting treatment drugs.
 - Male patients must agree to use an adequate method of contraception for the duration of the study and for 90 days after study therapy discontinuation.
 - Female patients must be either post-menopausal, free from menses \geq 2 yrs, surgically sterilized, willing to use two adequate barrier methods of contraception to prevent pregnancy, or agree to abstain from sexual activity starting from screening and continuing through 90 days after study therapy discontinuation.

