 - Female patients of child bearing potential must agree to comply with the fertility and pregnancy test requirements dictated by the Rev-Assist program.\

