5.8 Schedule of Tests and Observations

5.8.1 Screening

Medical history & clinical examination, ECOG/WHO PS, vital signs, concomitant medications, date of diagnosis, previous treatment, and appropriate assessment of inclusion and exclusion criteria will be performed within 4 weeks prior to starting protocol-based therapy.

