9.2 LENALIDOMIDE (Revlimid™)

Lenalidomide (REVLIMID®), a thalidomide analogue, is an immunomodulatory agent with anti-angiogenic properties. The chemical name is 3-(4-amino-1-oxo 1,3-dihydro -2H-isoindol-2-yl) piperidine-2,6-dione. Lenalidomide has been studied extensively in myeloma and it is approved for use in newly diagnosed and in relapsed MM.

Supply: REVLIMID® (lenalidomide) is available in 5, 10, 15 and 25 mg capsules for oral administration. Each capsule contains lenalidomide as the active ingredient and the following inactive ingredients: lactose anhydrous, microcrystalline cellulose, croscarmellose sodium, and magnesium stearate. The 5 mg capsule shell contains gelatin, titanium dioxide and black ink. The 10 mg capsule shell contains gelatin, FD&C blue #2, yellow iron oxide, titanium dioxide and black ink.

Elimination: The metabolic profile of lenalidomide in humans has not been studied. In healthy volunteers, approximately two-thirds of lenalidomide is eliminated unchanged through urinary excretion. The process exceeds the glomerular filtration rate and therefore is partially or entirely active. Half-life of elimination is approximately 3 hours.

Pregnancy: Due to its structural similarities to thalidomide, a known human teratogen, lenalidomide is contraindicated in pregnant women and women capable of becoming pregnant. When there is no alternative, females of childbearing potential may be treated with lenalidomide provided adequate precautions are taken to avoid pregnancy. Females must commit either to abstain continuously from heterosexual sexual intercourse or to use two methods of reliable birth control, including at least one highly effective method (e.g., IUD, hormonal contraception, tubal ligation, or partner's vasectomy) and one additional effective method (e.g., latex condom, diaphragm, or cervical cap), beginning 4 weeks prior to initiating treatment with REVCLIMID® (lenalidomide), during therapy with REVCLIMID® (lenalidomide), during therapy delay, and continuing for 4 weeks following discontinuation of REVCLIMID® (lenalidomide) therapy. If hormonal or IUD contraception is medically contraindicated, two other effective or highly effective methods may be used.

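### The contraception bullet in both eligibility lists accepts two barrier methods, while section 9.2 requires a highly effective method from 4 weeks before lenalidomide

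*Combined protocol and SAP*

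**What the plan says.** **Eligibility lists.** The fertility requirements in section 3.1 give several alternatives for female patients. Besides menopause and surgical sterilization, a woman may qualify by being "willing to use two adequate barrier methods of contraception to prevent pregnancy, or agree to abstain from sexual activity starting from screening". The synopsis has the same option: "willing to use two adequate barrier methods of contraception to prevent pregnancy". That bullet attaches no condition on when a barrier-only choice is acceptable. The period after treatment is 90 days.

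**Section 9.2, Pregnancy.** The rule for lenalidomide reads "Females must commit either to abstain continuously from heterosexual sexual intercourse or to use two methods of reliable birth control". The first of the two methods is then specified as "including at least one highly effective method (e.g., IUD, hormonal contraception, tubal ligation, or partner's vasectomy". For the second method and for the start date, the section goes on to say "and one additional effective method (e.g., latex condom, diaphragm, or cervical cap), beginning 4 weeks prior to initiating treatment". There is one exception: "If hormonal or IUD contraception is medically contraindicated, two other effective or highly effective methods may be used". After lenalidomide stops, section 9.2 asks for 4 weeks.

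**Screening.** Section 5.8.1 says that screening procedures "will be performed within 4 weeks prior to starting protocol-based therapy". It gives no minimum interval.

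**Rev-Assist.** The next bullet in section 3.1 adds that women of childbearing potential "must agree to comply with the fertility and pregnancy test requirements dictated by the Rev-Assist program"; the synopsis has a matching bullet. Footnote l of the Schedule of Events (5.8.6) makes lenalidomide prescribing conditional on that program. Appendix F reproduces the prescribing steps. On contraception it asks only for counselling on an appropriate method.

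**Pregnancy test.** The synopsis places the negative test no later than 7 days before treatment. Section 3.1 places it inside the 7 days before treatment.

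**The concern.** Section 9.2 contraindicates lenalidomide in pregnancy and allows women of childbearing potential to be treated only with adequate precautions. It then defines those precautions. The eligibility bullet defines them differently, and less strictly on the type of method. A woman who relies on two barrier methods and has no medical reason to avoid hormonal or intrauterine contraception satisfies the bullet but not section 9.2.

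Eligibility lists are what sites work from. Section 7.5 asks subsites to supply source documents for each inclusion and exclusion criterion at registration, so the bullet is among the statements that get verified. Pregnancy testing is no substitute for the rule, because a test finds a pregnancy only after conception. What is at stake is fetal exposure to a drug related to a known human teratogen. The response-rate design, the endpoints and the analysis are not affected.

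**Working it through.** There is no planned figure to reproduce. The check sets the texts side by side.

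1. **Type of method.** The bullet in the synopsis and in section 3.1 accepts two barrier methods, so it requires no highly effective method. Section 9.2 requires at least one by default. Its examples of highly effective methods are an intrauterine device, hormonal contraception, tubal ligation and a partner's vasectomy. Condom, diaphragm and cervical cap appear only as examples of the second, additional method. Two barriers therefore do not meet the section 9.2 default.

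2. **Exception.** Section 9.2 lets a woman use two other effective methods if hormonal or intrauterine contraception is medically contraindicated. Two barriers could qualify under that clause. The bullet offers the same choice without the contraindication, so it turns an exception into a general option.

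3. **Start date.** Section 9.2 starts contraception 4 weeks before lenalidomide. In the bullet, the phrase about starting at screening may belong to abstinence alone or to the barrier methods as well. Take the reading kinder to the lists, in which it covers both. Section 5.8.1 caps the time from screening to treatment at 4 weeks and sets no minimum. The 4-week lead is then met only if screening falls at the earliest permitted point. On the other reading, the bullet gives no start date for barrier methods. Neither reading guarantees the lead.

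4. **Does another text settle it?** The Rev-Assist bullet and footnote l add a condition. Appendix F, the only Rev-Assist text in the documents, gives pregnancy-test timing, surveys, authorization numbers and counselling, but no required method and no 4-week contraceptive lead. It does not say which of the two rules applies.

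5. **Period after treatment.** Here the lists are the stricter text: 90 days against 4 weeks in section 9.2. The conflict is limited to the type of method and the start date.

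6. **Pregnancy test.** The synopsis and section 3.1 point in opposite directions from the 7-day mark. Section 10.6 requires testing as the program demands, footnote d requires a negative result before lenalidomide on day 1 of each cycle, and Appendix F requires one test 10 to 14 days and another within 24 hours before the first prescription. The synopsis wording is a drafting error with little practical effect.

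**The case against.** The strongest reply is that the contraception bullet never acts alone. Women of childbearing potential must also accept the Rev-Assist fertility requirements, and footnote l means lenalidomide cannot be prescribed outside the program. Appendix F adds a signed patient-physician agreement, mandatory counselling, patient and prescriber surveys and a new authorization number for each prescription. Section 9.2 is itself binding protocol text, and nothing says that the lists override it. The lists can be read as layers: a general study rule that runs for 90 days after treatment, plus a lenalidomide-specific bullet. Subsites that verify every criterion must verify the Rev-Assist bullet too.

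Most of this stands, and it limits what can be claimed. A reader might infer that a woman using barriers only would receive lenalidomide with nothing to stop her. The documents do not support that, because the program and section 9.2 both stand in the way. Nor does the brevity of Appendix F show that Rev-Assist has no rule on methods: it refers to an agreement form that is not reproduced.

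What the reply does not do is remove the contradiction. Layering would work if the bullet were silent on method, but it names a method pair that section 9.2 accepts only by exception. A site reading the protocol alone cannot tell which text governs.

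**Conclusion.** The point holds as an internal contradiction on a safety rule. Both eligibility lists treat two barrier methods as sufficient. Section 9.2 does not, unless hormonal or intrauterine contraception is contraindicated, and the lists do not secure its 4-week lead. Confidence in the textual conflict is high. Whether a patient would in practice be treated on the weaker rule cannot be determined from the documents, since the full Rev-Assist requirements are not in them.

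Two stronger readings should be resisted. A reader might subtract the screening window from the 4-week lead and report the result as days of unprotected exposure. That would be a difference between two permitted windows, and it would assume that section 9.2's own start rule is ignored. The number of women of childbearing potential is also not given, so no exposure or shortfall is claimed here. A reader might also treat the synopsis test window as a safety gap. The other testing rules already require tests close to dosing, so it is only a wording correction.

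The correction should be made. The conclusion assumes that section 9.2 states a rule for this trial and is more than product background. Its mandatory phrasing supports this, as does its requirement of thrombosis prophylaxis for patients enrolled in this trial.

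**What to change.** - In the synopsis and section 3.1, for women of childbearing potential, replace the two-barrier option with the section 9.2 rule: continuous abstinence, or one highly effective method plus one additional effective method, from 4 weeks before lenalidomide. Include the exception for women in whom hormonal or intrauterine contraception is medically contraindicated.
- Keep the 90-day period after treatment, which is longer than section 9.2 requires.
- Keep the Rev-Assist bullet.
- In the synopsis, change the pregnancy-test window to the 7 days before treatment, as in section 3.1.

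The cost is an amendment to wording in two places, with no added tests. The one downside is that a woman not already using a compliant method may have to wait up to 4 weeks before starting, and section 9.2 already requires that wait.

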3.2 Exclusion Criteria

- Patients with peripheral neuropathy $>$ CTCAE grade 2
- Patients receiving concurrent corticosteroids for reason(s) other than for physiologic maintenance treatment. Patients should otherwise discontinue corticosteroids prior to registration to study.
- History of allergic reaction (including erythema nodosum) to lenalidomide
- Concurrent use of complementary or alternative medicines that would confound the interpretation of toxicities and antitumor activity of the study drugs.
- Patients with contraindication to thromboprophylaxis.
- Unacceptable cardiac risk factors defined by any of the following criteria: Patients with congenital long QT syndrome, any history of ventricular fibrillation or torsade de pointes, bradycardia defined as HR $<$ 50 bpm, Left ventricular ejection fraction $<$ 30%.

- Patients who have received targeted or investigational agents prior to registration within 2 weeks or within 5 half-lives of the agent and active metabolites (whichever is longer) and who have not recovered from side effects of those therapies.
- Patients who have undergone major surgery \leq 2 weeks prior to registration to study or who have not recovered from the side-effects of surgery.
- Patients with known positivity for human immunodeficiency virus (HIV), or hepatitis C. Baseline testing for HIV and hepatitis C is not required
- Patients with a history of another primary malignancy that is currently clinically significant or currently requires active intervention, other than non- melanoma skin cancer and carcinoma in situ of the cervix should not be enrolled. Patients are not considered to have a “currently active” malignancy if they have completed therapy for a prior malignancy, are disease free from a prior malignancy for \geq 5 yrs and are considered by their physician to be less than 30% risk of relapse.
- Patients with active (untreated or relapsed) CNS metastasis of the patient’s myeloma.
- Patients with a history of gastrointestinal surgery or other procedure that might, in the opinion of the investigator(s), interfere with the absorption or swallowing of the study drugs.
- Patients with any significant history of non-compliance to medical regimens or unwilling or unable to comply with the instructions given to them by the study staff.
- Any other medical condition, including mental illness or substance abuse, deemed by the investigator(s) to likely interfere with the patient’s ability to sign informed consent, cooperate and participate in the study, or interfere with the interpretation of the results.

3.3 Inclusion of Women and Minorities

Both men and women of all races and ethnic groups are eligible for the study.

4 STUDY DESIGN AND DURATION

4.1 Study Design

This is a non-randomized open-label phase I/II study for patients with relapsed and refractory multiple myeloma. For the phase I part, we will conduct a standard 3+3 design over 4 main dose levels cohorts evaluating 1.5, 3, 3, and 6 mg/kg of CT-011 given intravenously every 4 weeks (every 28 days) on day 3, and lenalidomide given at 15, 15, 25, and 25 mg orally daily on days 1-21 of a 28-day cycle, to determine the maximum tolerated dose. The phase II will commence once the MTD is determined, and this dose level combination for CT-011 and lenalidomide will be used for the phase II portion of this trial. Patients will be assessed for response at the end of cycle 4 or sooner if necessary according to the IMWG response criteria.

4.2 Definition of Dose Limiting Toxicity

For the phase I portion, patients will be monitored for safety by assessing toxicities as graded by the NCI CTCAE v4.0. The maximum tolerated dose (MTD) or dose limiting toxicity (DLT) will be defined as one or more of the following toxicities considered to be at least possibly related to one of the study drugs during Cycle 1:

- Grade 3 or greater non-hematologic toxicity with the exception of Grade 3 nausea, vomiting and diarrhea that responds to supportive therapy.
- Grade 4 thrombocytopenia, or grade 3 thrombocytopenia with bleeding, or any requirement for platelets transfusion

- Grade 4 neutropenia persisting for more than 5 days.
- Grade 3 or greater febrile neutropenia (temperature $\geq 38.5^{\circ}\text{C}$)
- Grade 4 anemia, unexplained by underlying disease

